## 7.573 Patient Monitoring

Patients will be monitored carefully by CES for any change in their clinical status, using reports of seizure frequency, adverse events and toxicity at regular patient contact about once every 2 weeks, and clinical exam, laboratory studies, and Hamilton Depression rating scale at clinic visits. Criteria to be used to decide whether a report or test result requires intervention include Grade 3 NCI CTC toxicity, a laboratory test twice the upper limit of normal, an abnormal finding on EEG or ECG not present at baseline, or an increase of 7 on the Hamilton Depression Scale. Intervention will be determined by the safety monitor and may include consultation, additional studies, or withdrawing the patient from the protocol.

## 7.58 Description of procedures

### 7.581 Neuropsychological and Mood Assessments

#### Attention:

Brief Test of Attention (Schretlen 1997)  
Cancellation test from the WAIS-IV (Wechsler 2008).

#### Memory:

Hopkins Verbal Learning Test, versions 1,3 &4 (Brandt and Benedict 2001).  
Brief Visuospatial Memory Test-Revised (Benedict 1997)

#### Executive Functions:

Controlled Oral Word Association Test: 3 different forms (FAS, CFL, PRT) (Spren and Strauss 1998)  
Trail Making Test (Spren and Strauss 1998)  
Design Fluency (Delis et al 2001).

#### Mood rating scales:

Hamilton Depression Rating Scale-24 item  
Hamilton Anxiety Rating Scale  
Beck-2 Depression Self Inventory  
Columbia Suicide Severity Rating Scale

### 7.582 PET Scan:

A PET scan with 18F-FCWAY and a transmission scan will be performed once (if patients have not had them already) in a single session before initiation of study drug.

For the PET scans, patients will be in a fasting state for three hours prior to the procedure. Patients may not use any alcohol or recreational drugs for the two weeks preceding the PET scan. EEG leads may be attached to the scalp to record EEG during the PET scan if warranted by the patient's seizure pattern. The thermoplastic facemask will be used in the standard manner for NIH PET scans. An IV infusion of 0.9% saline solution will be started to provide IV access for radiotracer administration.

Following transmission scans, 10 mCi of [F-18]FCWAY will be administered. Scanning will proceed for 120 minutes. If necessary, scanning can be interrupted to allow the patient to sit up and rest, and resumed for the remainder of the predetermined time.

During the [F-18]FCWAY study, up to 40 arterial blood samples (approximately 250 cc) will be collected and radioactivity concentration in whole blood and plasma will be determined. A catheter will be placed in the patient's radial artery by the NIH Anesthesia Department. The skin at the site of the puncture will be anesthetized with 1% lidocaine. The catheter will be perfused (3ml/hr) with heparin solution (600 units/l) during the procedure. The amount of heparin infused will be much smaller than the amount necessary to produce any systemic anticoagulant effect. The arterial input function is necessary for quantitation of 5HT1A receptor volume of distribution. In addition, at selected sample times, samples will be used to measure the fraction of the radioactivity in plasma that has not been metabolized. The fraction of plasma radioactivity unbound to protein will also be determined.

Scans will be performed with the PET/CT or the High Resolution Research Tomograph (HRRT). The slice separation is 2.0 mm. The transverse resolution is 4.4 mm in HIREZ and the axial resolution is 4.5 mm in HIREZ. All scans will be acquired in 3D mode and start with an 8-min transmission scan with 2 rotating rod sources for the purpose of attenuation correction.

Blood samples for cortisol and ACTH level will be obtained at the time of PET, through the A line or IV line.

IV and arterial catheters will be removed after scanning is completed. The patient will be asked to urinate after the scan and again two hours later.

7.583 Genetic Testing:

Testing for polymorphisms in genes related to serotonin transport, depression, and epileptogenesis

If patients have not provided DNA samples previously, we will obtain saliva samples to test for polymorphisms in SERT, TPNH, COMT, BDNF and GABA genes that have been associated with psychiatric disorders and epileptogenesis. DNA testing is optional.

Samples and data may be used for comparison with samples from epilepsy patients and normal controls obtained in future studies.

DNA and cell lines will be processed, tested for polymorphisms, and maintained in the Laboratory of [name], NIAAA, using the established procedures of his laboratory.

7.584 Total blood to be drawn

Screen	Baseline	Treatment Phase Period 1 6 Weeks (+/- 2 weeks) and 12 -16 Weeks	Wash out 4-6 weeks	Treatment Phase Period 2 6-weeks (+/- 2 weeks) and 12-16 Weeks	Approx. 1 month post study follow up
Acute care panel and Hepatic panel 10 mL	AED level 8 – 16 mL	Acute care panel and Hepatic panel 30 mL		Acute care panel and Hepatic panel 30 mL	Acute care panel and Hepatic panel 8 mL
CBC 3 mL	ACTH 2 mL Done with PET	CBC 9 mL		CBC 9 mL	CBC 3 mL
AED level 8 – 16 mL	Cortisol 10 mL Done with PET	AED level 24 - 48 mL		AED level 24 – 48 mL	AED level 8 – 16 mL

	PET study 250 mL				
Max 29 mL	Max 278 mL	Max 87 mL		Max 87 mL	Max 29 mL

## 7.6 Follow-up and termination procedures

### 7.61 Transfer / Continuity of care

During the study, AEDs will be managed by NINDS neurology staff. At the end of the study, patients may be considered for inclusion in additional NINDS protocols. If they do not qualify or wish to participate, they will be referred to the care of their referring physicians. Patients who do not have a referring physician or wish to find an alternative will be assisted in locating a neurologist skilled in the care of people with epilepsy.

### 7.62 Information to be shared with subjects or health care providers

All clinical data obtained during screening, as well as any other data relevant to standard epilepsy care obtained during the protocol, will be shared with patients and with the participant's written permission, their health care providers.

## 7.7 Research and clinical care procedures

All procedures performed under this protocol are research-related.

[figure not shown]
### 7.71 Medications requiring IND

18F-FCWAY: Sponsor NIH PET Department. Approved  
 PRX-00023: Sponsor [name] MD. Approved

### 7.72 Study Drug (see Investigator's Brochure).

INN: Naluzotan  
 CAS number: [740873-07-08]  
 Molecular weight: 537.57 g/mol  
 Empirical formula: C23H38N4O3S2·2HCl  
 Chemical name: N-{3-[4-(4-cyclohexylmethanesulfonylamino-butyl)-piperazin-1-yl]-phenyl}-acetamide dihydrochloride

Chemical structure:

**PRX-00023**

Following ascending multiple oral PRX-00023 dose titration, absorption of PRX-00023 was fairly rapid (Tmax one to four hours) and mean serum concentrations appear to increase with

increasing doses of 80 to 320mg QD or 40 mg BID to 160 mg BID, respectively. Elimination half-life is estimated to be 9.8 to 13.5 hours. Plasma protein binding is approximately 90%.

PRX-00023 is metabolized mainly by CYP 3A4 and to a lesser extent by CYP 2D6. It may interact with inducers such as phenobarbital or phenytoin. Felbamate, oxcarbazepine, and topiramate are weak inducers of the CYP isoenzyme 3A4, and would be less likely to alter the metabolism of PRX-00023. For carbamazepine, potential induction of metabolism may be balanced by inhibition of PgP brain efflux transport, for which PRX-00023 is a substrate. PRX-00023 does not to inhibit or induce any CYP enzymes.

### 7.73 Source of materials/storage/handling

Trial Product Compound Product Name	PRX00023 PRX-00023 (Naluzotan)
Dosage Route Strength Manufacturer	Oral Capsule 37.2mg (equivalent to 40mg bis salt) Clinical Center Pharmacy Department [name]
Comparator Product Manufacturer	PRX-00023 Placebo capsule Clinical Center Pharmacy Department [name]

Drug Substance (API) has been manufactured by Johnson Matthey Pharma Services, [name] in accordance with the Clinical Trials Directive 2001/20/EC, GMP Directive 2003/94 and 21 CFR Parts 210 and 211 for Investigational Medicinal Products.

The NIH Pharmacy will dispense three month's supply of study drug (PRX-002 or placebo) to subjects. Patients will be encouraged to bring pill bottles to each visit. If patients bring pill bottles, pill counts will be performed. Patients will be advised to take a missed dose they remember within 4 hours; otherwise, to take the next scheduled dose and record the missed dose on their seizure calendar. Patients will be advised to take their study drug with food.

All unused investigational product will be returned to the NIH Pharmacy for disposal.

### 7.73 Radiation

All radiation administered under the protocol is for research only.

### 7.74 Relationship of this study to other protocols

Patients will be screened under protocol 01-N-0139.

#### 7.75 Storage of data and samples

Study data will be stored in password-protected NINDS and NIH Clinical Center computer systems.

DNA and cell lines will be maintained in the Laboratory of [name], NIAAA, using the established data protection procedures of his laboratory.

### 8. Risks and discomforts

#### 8.1 PRX-00023

PRX-00023 has been studied in approximately 100 healthy human volunteers and in 340 patients with generalized anxiety disorder (GAD) and major depression disorder (MDD). Safety data for doses up to 320 mg per day have been reported. The most common side effects include headache, dizziness, nausea, diarrhea, dyspepsia and insomnia. In clinical trials, 5-10% more patients on active drug than on placebo reported at least one side effect (see section 4.42). Drug side effects are expected to be transient, and respond to dose reduction if necessary.

Considering PRX-00023 pharmacokinetics, patients not on the AEDs listed in exclusion criteria are considered unlikely to show significant drug interactions, although unexpected risks are possible.

A possible small increase in 'suicidality' has been associated with SSRIs and AEDs but not direct 5HT1A agonists.

The potential risk for birth defects in children of parents taking PRX-00023 is unknown. Men and Women must use an effective method of contraception during the study and for three months afterwards. If a woman becomes pregnant, she will be dropped from the study and the blind will be broken. Appropriate counseling will be provided.

PRX-00023 has not been given to patients with epilepsy. Risk will be minimized by screening for exclusion criteria, and careful clinical monitoring, weekly contact, and at each clinic visit.

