## 7.4 Study design

Following screening and a baseline phase (up to 6 weeks), patients will enter a treatment phase of 2 periods (Period 1 and Period 2) with a washout phase between periods 1 and 2. If patients have 4 seizures in less than six weeks during the baseline phase, they do not need to wait the entire 6-weeks to begin the treatment phase (Period 1) of the study. Each treatment period will last approximately 12-16 weeks. Following Period 1, there will be a wash-out of 4 – 6 weeks where no study medication will be taken. During each treatment period, there will be two Clinical Center visits. The first visit will entail clinical assessments and will occur 6-week +/- 2 weeks after starting the study drug and the second visit will entail clinical assessments and neuropsychological and mood assessment and will occur at the end of each maximum tolerated dose (MTD) treatment period. In addition, a follow-up visit will occur approximately one month following the end of the second treatment period that will include a physical examination and review of any adverse events. The total duration of the study is 42-46 weeks (+/- 4 weeks). Each clinic visit will last approximately one hour. The neuropsychological and mood evaluation at the end of each treatment period will last up to three hours.

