#### 7.52 Randomization to Active drug or Placebo

Subjects will be randomized at the end of baseline to either active drug or placebo using a 1:1 ratio per the randomization schedule. The randomization schedule will be generated, secured, distributed, and stored by the NIH Pharmacy. Patients may be outpatients or inpatients during titration depending on their geographical location, need for additional education on the titration process or if they are participating in concurrent studies with the Clinical Epilepsy Section. All patients will be given an exact written titration schedule to follow.

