#### 7.53 Period 1:

During Period 1 there will be regular communication with patients/families by phone, secure email, and/or the clinical trial database. Communication with patients/families will occur approximately 6 times during each treatment period, about once every two weeks.

PRX-00023 or matching placebo will be titrated up starting at an oral dose of 40 milligrams (Mg) twice daily for five days; the dose will then be increased to 80 milligrams twice daily for five days, and then to 120 milligrams twice daily for approximately 70 days. After which the dose will be tapered off as follows: 80 milligrams twice daily for five days, 40 milligrams twice daily for five days, followed by discontinuation of study drug. If patients experience side effects during the titration up, the next scheduled dose increase will be delayed until they abate. If this does not occur, the dose will be reduced in 40mg per day increments. Period 1 will last approximately 12-16 weeks. The above description and table below provides a targeted dosing schedule, however, adjustments may be made if, for example, the patient experiences side effects during titration.

	Titration		MTD	Taper	
Day	Day 0-4	Day 5-9	Day 10-79	Day 80-84	Day 85-90
No. of days	5 days	5 days	70 days	5 days	5 days
Dose	40mg bid	80mg bid	120mg bid	80mg bid	40 mg bid

Patients will keep seizure calendars. Patients will return to NIH 6 weeks +/- 2 weeks after the start of Period 1 and the tests listed in section 7.571 will be performed. At the end of the Maximum Tolerated Dose (MTD) period, patients will again return to NIH for repeat of baseline testing (see section 7.572). Following testing, patients will be tapered off of Period 1 study drug and begin washout period.

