#### 7.54 Washout Period

Following the completion of Period 1, there will be a washout period for approximately 4 to 6 weeks.

#### 7.55 Period 2

Following a washout period, patients will be crossed over to the alternative treatment arm, using the same titration schedule as for Period 1. Patients may be outpatients or inpatients during titration. Outpatients will be given an exact written titration schedule to follow. During Period 2, there will be regular communication with patients/families by phone, secure email and/or the clinical trial database. Communication with patients/families will occur approximately 6 times during treatment Period 2; about once every two weeks. Patients will keep seizure calendars. Patients will return to NIH 6 weeks +/- 2 weeks after the start of Period 2 and the tests listed in section 7.571 will be performed. At the end of the Maximum Tolerated Dose period, patients will again return to NIH for repeat of baseline testing (see section 7.572). Following testing, patients will be tapered off of Period 2 study drug..

The same titration, MTD treatment, and taper schedule as described in Period 1 will be used for Period 2. Period 2 will last approximately 12-16 weeks..

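### Section 8.1 relies on weekly contact, section 7 schedules contact about every two weeks, and no section requires a check before the Day 5 and Day 10 dose increases

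*Combined protocol and SAP*

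**What the plan says.** Section 8.1 of the combined protocol and SAP states that the drug is new to patients with epilepsy. It lists the measures that will limit risk: screening against the exclusion criteria, and "careful clinical monitoring, weekly contact, and at each clinic visit".

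The procedural sections give a different interval:

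- 7.53 (Period 1): "Communication with patients/families will occur approximately 6 times during each treatment period, about once every two weeks".
- 7.55 (Period 2): "Communication with patients/families will occur approximately 6 times during treatment Period 2; about once every two weeks".
- 7.573 (Patient Monitoring): seizure frequency, adverse events and toxicity are reported "at regular patient contact about once every 2 weeks".
- 9.1 and 16 refer to contact or communication with patients without giving an interval.

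On titration, the 7.53 dosing table has 40 mg bid on Days 0-4, 80 mg bid on Days 5-9 and 120 mg bid from Day 10. Period 2 uses the same schedule. The safeguard is that "If patients experience side effects during the titration up, the next scheduled dose increase will be delayed until they abate". Section 7.52 covers the setting: "Patients may be outpatients or inpatients during titration depending on their geographical location", among other grounds. It adds: "All patients will be given an exact written titration schedule to follow". For the first on-treatment clinic visit, 7.4 says: "The first visit will entail clinical assessments and will occur 6-week +/- 2 weeks after starting the study drug".

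**The concern.** There are two linked problems.

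First, the risk section of a study classed as more than minimal risk (section 14) names a safeguard that the procedures do not deliver. Staff cannot follow both intervals, and anyone weighing risk from 8.1 would believe that contact is twice as frequent as planned.

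Second, titration is when a check matters most, and none is required. The delay rule in 7.53 works only if someone learns of side effects before the next step. An outpatient holds a written instruction to increase the dose, and no section obliges staff to ask first. The rule then depends on the patient reporting unprompted.

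The protocol's own data give a reason to look before each step. In Table 2 of 4.42, moving from doses of 90 mg or less to 120-150 mg, headache goes from 4% to 18.4%, dizziness from 6.9% to 15.7% and nausea from 5.9% to 15.7%. The target here, 240 mg per day, is above both bands. Section 16.1 also treats a rise in seizures to more than three times baseline as grounds for stopping if it occurs in more than half of patients, so worsening seizures are a recognised possibility.

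**Working it through.** **Inputs.** Weekly contact (8.1); about two-weekly contact, about 6 per period (7.53, 7.55, 7.573); period length 12-16 weeks (7.53, 7.55); increases on Days 5 and 10 (7.53 table); first clinic visit at 6 weeks ± 2 weeks (7.4).

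**The plan's own figure.** 12 weeks / 2 = 6 contacts, which matches the stated 6 or so for a 12-week period. At 16 weeks, a two-week interval gives 16 / 2 = 8, and 6 contacts would be 16 / 6 = 2.7 weeks apart.

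**Contacts per period**

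| Period length | Weekly (8.1) | Two-weekly (section 7) | Ratio |
|---|---|---|---|
| 12 weeks | 12 | 6 | 2 |
| 16 weeks | 16 | 8 | 2 |

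**Contacts before each increase**

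| | Section 7 as written | Weekly, counted from Day 0 |
|---|---|---|
| Before Day 5 (80 to 160 mg/day) | 0 required | 0 |
| Before Day 10 (160 to 240 mg/day) | 0 required | 1 (Day 7) |

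**Does the date of the first contact rescue the two-weekly schedule?** The sections give no date, so take any. A check before the first increase must fall in Days 0-4, and a check between the two increases in Days 5-9. Both windows lie within Days 0-9, and the widest gap between a day in one and a day in the other is 9 - 0 = 9 days. Contacts 14 days apart can therefore fall in at most one of them. If the first contact came one interval after the start, on Day 14, it would fall in neither, 14 - 10 = 4 days after the second increase.

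**Does the clinic visit fill the gap?** Earliest visit: (6 - 2) × 7 = Day 28. That is 28 - 10 = 18 days after the second increase.

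**Does weekly contact alone fill it?** Counted from Day 0, the first weekly contact is on Day 7. It precedes the Day 10 increase but follows the Day 5 one. Putting weekly contact into section 7 would remove the contradiction but would not reliably cover both steps.

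**The case against.** The strongest reply is that the contradiction is editorial. Three operative sections agree on about two weeks, the outlier is one phrase in a narrative risk section, and staff following section 7 have a clear schedule. On this view the pre-increase check is a separate design preference. Titration already has protections: increases can be delayed and doses reduced (7.53); inpatient titration is possible, including where a patient needs more education on the process (7.52); adverse events are recorded when patients report them (11.3); there are toxicity rules (9.2) and an independent medical monitor (16). The earlier depression trial (CP-020, section 4.42) titrated faster, reaching 120 mg bid on Day 8. Serious adverse events occurred in 0.6% on drug against 2.2% on placebo, and none was considered treatment related. The Study Calendar listed in section 26 is not in the text available and might include titration calls; an approximate two-week interval does not forbid an earlier one.

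Much of this limits the size of the concern without removing it. The two parts are indeed separate, and correcting 8.1 would settle only the first. The protections are real but partial: inpatient titration is optional, and the delay rule still needs someone to learn of the side effect. The depression trial is reassuring about tolerability, but its patients did not have epilepsy, which is the gap 8.1 itself points out. A calendar with titration calls could close the second part in practice. It would not reconcile 8.1 with section 7.

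**Conclusion.** Both parts hold. Section 8.1 claims contact twice as often as section 7 schedules, and no section of the protocol requires contact before either dose increase. On the target schedule an outpatient can go from 80 to 240 mg per day by Day 10 with no scheduled contact, and with no clinic visit until Day 28 at the earliest.

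This rests on the protocol sections alone, since the Study Calendar was not available, and on the target dosing dates in 7.53. No date for the first contact is assumed. That both increases precede it is something the plan permits, not something it prescribes. Patients titrated as inpatients are much less affected.

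The consequence is confined to safety monitoring. Seizures are recorded on calendars throughout, and no sample size, power or analysis figure changes. The correction should be made because it is cheap and makes the plan's own delay rule workable.

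**What to change.** Amend 7.53 and 7.55 to require a check of side effects and seizures by phone or email on about Day 4 and Day 9, in both periods, with each increase going ahead only after the check. For inpatients, the ward review counts. Period 2 needs the same checks because patients given placebo first meet the active drug there.

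After titration, keep the two-weekly contact that section 7 already plans, unless the investigator prefers weekly. State the resulting schedule identically in 7.53, 7.55, 7.573 and 8.1.

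Cost: one protocol amendment and 2 contacts × 2 periods = 4 per outpatient. That is at most 4 × 20 = 80 for 20 completers, or 4 × 30 = 120 for 30 patients, made by existing staff; inpatients need none. The drawback is a less reassuring sentence in 8.1 if contact is two-weekly after titration, or a larger contact load if weekly contact is adopted throughout.

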#### 8.2 PET

PET scans require exposure to radiation. All tests requiring patient exposure to ionizing radiation should be considered to be potentially hazardous. Detailed breakdown of the radiation exposures to be expected in subjects enrolled in this protocol are included in the attached radiation safety form (NIH 88-23(a) revised). Although each organ will receive a different dose, the amount of radiation exposure is equal to a uniform whole-body exposure of 0.77 rem. This calculated value is known as the "effective dose" and is used to relate the dose received by each organ to a single value. The doses to be administered have been approved by the NIH radiation safety committee. The total anticipated 'effective dose,' equivalent to whole-body exposure, is less than the RSC exposure limit for research subjects of 5.0 REM per year. Some patients may become uncomfortable while lying in the scanner.

